We will also compare relevant patient-reported outcomes (PROs) across the three intervention arms (secondary outcomes). We will assess knowledge about and confidence in follow-up care using the Preparing for Life as a (New) Survivor (PLANS); cancer worry and health worry with the Assessment of Survivor Concerns (ASC); and information needs with the Follow-up Care Use among Survivors (FOCUS) questionnaire.

AIM 3: Assess patients' perspectives on the value of survivorship care planning

We will conduct qualitative interviews with a subset of patients (n=40) to assess which aspects of the SCP process are most valued and explore whether there are different perspectives on the value of SCPs between institutions or by cancer type or study arm. This aim is not included in this protocol. It will be submitted as an amendment as the interview guide will be informed by the implementation of the trial.

Data from the 3 aims will identify attributes of SCP models and implementation processes that can be used to promote feasible and effective patient-centered survivorship care planning processes across a range of clinical settings, cancer types, and populations served. Determination of the preferable mode of SCP delivery will be based off of the primary endpoint (receipt of recommended follow-up care over 18 months).

3. Background (briefly describe pre-clinical and clinical data, current experience with procedures, drug or device, and any other relevant information to justify the research)

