- Not treated with intent to cure;
- Did not have cancer care primarily managed within one of the 4 participating clinics, or JHMI or PRMC oncology program practices are not primarily responsible for the patients’ survivorship care;
- Does not have health insurance at screening; and
- Enrolled in a competing and/or conflicting research trial at the time of enrollment.

6. Drugs/ Substances/ Devices

Not applicable

7. Study Statistics

a. Primary outcome variable.

The primary endpoint of this study will be the proportion of patients who receive appropriate cancer-related follow-up care (based on the individual's SCP). The outcome will be operationalized as a dichotomous variable (received recommended care: yes/no). This endpoint will be used to determine the preferable delivery modality (study arm).

b. Secondary outcome variables.

Secondary outcomes of health service use include (1) receipt of appropriate primary and preventive care and (2) not receiving tests that are not recommended. These outcomes will also be operationalized as a dichotomous variable (received recommended primary/preventive care: yes/no; did not receive inappropriate care: yes/no). In addition to the dichotomous outcomes, we will also examine receipt of individual care services. For example, the primary dichotomous outcome for colorectal cancer patients may include receipt of colonoscopy and CEA testing; as a secondary outcome, we will also examine receipt of each of those services separately.

Patient-reported outcomes (PROs) are also important secondary outcomes. Participants will complete PRO measures assessing survivorship knowledge and confidence, worry, and information needs at baseline, 6-months, 12-months, and 18-months post treatment completion. Based on a review of the literature and consultation with the survivor members of our Stakeholder Advisory Board, the PRO assessment will include three instruments:

- Preparing for Life as a (New) Survivor (PLANS): The PLANS survey includes 11 knowledge items rated on a 4-point Likert scale from 1=strongly disagree to 4=strongly agree, as well as 5 confidence items rated on a 10-point scale from 1=not at all confident to 10=extremely confident, and an open-ended question. The PLANS was developed at the University of Michigan and was used by our team in a previous survivorship care planning evaluation (Dunn, R., Crowley, S., & Janz, N., 2011; Smith et al., 2016). The items are analyzed individually.

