Arm B	33	16	34	17	8	16
Arm C	33	17	33	16	9	17
Total	100	50	100	50	25	50

Previous studies show that patient adherence in the survivorship period is varied, depending on the cancer type and/or the particular health service being studied. We considered a range of adherence probabilities and varying differences between them among randomization arms. The operating characteristics of the design are shown in Table 3 below. Simulations (1,000) with varying values of the underlying probability of perfect adherence for each study arm provided the estimates in the table. For each simulation, responses for the primary endpoint were randomly drawn from a binomial distribution and compared between study arms with Fisher's exact test. Estimated power is the proportion of simulations that yielded a two-sided p value ≤ 0.05 . Table 3 shows that the study will have more than 80% power to detect differences ranging of about 5% and higher in the proportion of patients with perfect adherence among study arms. Table 3 also shows the power assuming 20% attrition, and even then, we have 80% power to detect differences of 10%-15% (and in some cases lower).

Table 3: Power Calculations for Primary Outcome

Total Sample Size (A / B / C)	Probability of receipt of outcome			Difference between arms	Estimated Power with Type I error = 5%
	Arm A	Arm B	Arm C		
125 / 125 / 125	30%	39.5%	49%	9.5%, 9.5%	79.2%
		37.5%	52.5%	7.5%, 15%	93.2%
		45%	60%	15%, 15%	99.7%
	50%	55%	70%	5%, 15%	88.1%
		65%	72.5%	15%, 10%	91.7%
		65%	80.0%	15%, 15%	99.7%
	70%	75%	87.5%	5%, 12.5%	91.6%
		77.5%	90%	7.5%, 12.5%	96.8%
		82.5%	92.5%	12.5%, 10%	99.3%
Total Sample	Probability of receipt of			Difference	Estimated

Size (A / B / C)	outcome			between arms	Power with Type I error = 5%
	Arm A	Arm B	Arm C		
100 / 100 / 100	30%	39.5%	49%	9.5%, 9.5%	68.7%
		37.5%	52.5%	7.5%, 15%	84.2%
		45%	60%	15%, 15%	98.8%
	50%	55%	70%	5%, 15%	78.7%
		65%	72.5%	15%, 10%	84.8%
		65%	80.0%	15%, 15%	98.5%
	70%	75%	87.5%	5%, 12.5%	82.2%
		77.5%	90%	7.5%, 12.5%	91.6%
		82.5%	92.5%	12.5%, 10%	97.7%

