DATA ANALYSIS: Comparing the three models of SCPs, we will examine whether there are differences between intervention arms in receipt of care as recommended on the SCP, regardless of whether the SCP was received ('intention to treat'), and also whether receipt of an SCP leads to appropriate care receipt, comparing those who received a SCP to those who did not. In both cases, the endpoint is the proportion of patients who receive all cancer-related follow up care. We will also examine each component of appropriate care individually (e.g., proportion receiving mammogram). Analysis will be by Fisher's exact test for differences between groups. To help quantitatively describe the differences between groups, we will also use binary or categorical logistic regression models as appropriate to estimate odds ratios with 95% confidence intervals. To account for the stratified randomization, we will also include a regression model that estimates the main SCP-type effect while adjusting for cancer type and recruitment site. Planned

subgroup analyses include examining differential outcomes by patient cancer type and recruitment site using interaction analyses. P-values for determining statistical significance of these interaction tests will be corrected for multiple comparisons using a Bonferroni approach.

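### The claimed 80% power for differences of about 5% is not what Table 3 shows: a 5-point difference has about 12% to 35% power, and 80% needs a gap of roughly 14 to 20 points

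*Combined protocol and SAP*

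**What the plan says.** Section 7.c (SAMPLE SIZE) describes simulations in which "responses for the primary endpoint were randomly drawn from a binomial distribution and compared between study arms with Fisher's exact test". It adds: "Estimated power is the proportion of simulations that yielded a two-sided p value ≤ 0.05". Table 3 then lists nine sets of arm rates, each at 125 and at 100 per arm, with a column of differences between arms and the estimated power.

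The text draws two conclusions. At full enrolment, "Table 3 shows that the study will have more than 80% power to detect differences ranging of about 5% and higher". With 20% attrition, "even then, we have 80% power to detect differences of 10%-15% (and in some cases lower".

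The endpoint decides the trial's main question. Section 2 states: "Determination of the preferable mode of SCP delivery will be based off of the primary endpoint". Section 7.a says the same. Section 7.c (DATA ANALYSIS) plans a Fisher "exact test for differences between groups" and names no pairwise procedure.

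**The concern.** The first conclusion takes the smallest entry in the difference column as the detectable difference. That column holds adjacent steps, A to B and then B to C. A 5% entry occurs in only two scenarios, 50/55/70 and 70/75/87.5, each time next to a B-to-C step of 15 or 12.5 points. A three-arm test gets its power from the whole spread of rates, so these rows say nothing about a trial in which the differences are about 5 points.

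These two sentences are the only summary of detectable difference for the primary endpoint. The arms rise in resource intensity, and section 4.e says that the aim is the simplest approach that is still effective. A non-significant result would therefore tend to favour the simplest arm. A reader who trusts the stated power could take such a result as evidence against a 5-point benefit, when the test would usually have missed one.

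**Working it through.** **Inputs.** Arm rates, arm sizes (125; 100 after 20% attrition), Fisher's exact test and two-sided 0.05, all from section 7.c and Table 3. The 5-, 10- and 15-point scenarios below are additional. They use Arm A rates from 30% to 70%, which is Table 3's own range.

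**Method.** For success counts a, b, c with n per arm and total m = a + b + c, the conditional probability is P(a,b,c | m) = C(n,a)·C(n,b)·C(n,c) / C(3n,m). The p-value is the sum of these probabilities over all tables with the same m that are no more probable than the observed one. Power is the sum of Bin(a; n, pA)·Bin(b; n, pB)·Bin(c; n, pC) over all tables with p ≤ 0.05. Every table was enumerated (126³ and 101³), so there is no simulation error.

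**Step 1: reproduce Table 3** (power in %, printed / recomputed).

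| A/B/C (%) | Printed steps | A-to-C gap | 125 per arm | 100 per arm |
|---|---|---|---|---|
| 30/39.5/49 | 9.5, 9.5 | 19 | 79.2 / 79.4 | 68.7 / 69.0 |
| 30/37.5/52.5 | 7.5, 15 | 22.5 | 93.2 / 92.2 | 84.2 / 84.9 |
| 30/45/60 | 15, 15 | 30 | 99.7 / 99.4 | 98.8 / 97.9 |
| 50/55/70 | 5, 15 | 20 | 88.1 / 86.5 | 78.7 / 77.4 |
| 50/65/72.5 | 15, 10 | 22.5 | 91.7 / 92.7 | 84.8 / 85.7 |
| 50/65/80 | 15, 15 | 30 | 99.7 / 99.7 | 98.5 / 98.8 |
| 70/75/87.5 | 5, 12.5 | 17.5 | 91.6 / 89.9 | 82.2 / 81.8 |
| 70/77.5/90 | 7.5, 12.5 | 20 | 96.8 / 96.7 | 91.6 / 91.9 |
| 70/82.5/92.5 | 12.5, 10 | 22.5 | 99.3 / 99.3 | 97.7 / 97.5 |

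The largest discrepancy is 91.6 − 89.9 = 1.7 points. The standard error of 1,000 simulations at that power is √(0.899 × 0.101 / 1000) = 0.0095, about 1 point, so this is ordinary simulation noise. Pairwise tests do not give the table: for 30/39.5/49 the A-B, B-C and A-C powers are 30.9%, 27.9% and 84.1%, against 79.2% printed. Table 3 is therefore three-arm omnibus power.

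**Step 2: power for 5-point differences, 125 per arm.**

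| Arm A rate | One arm alone +5 | B and C both +5 | Steps 5/5 |
|---|---|---|---|
| 30% | 12.6% | 12.5% | 29.3% |
| 50% | 11.5% | 11.6% | 27.2% |
| 70% | 13.2% | 13.4% | 34.9% |

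Over Arm A rates from 30% to 70% in 5-point steps, the ranges are 11.5% to 13.4% for one arm different and 26.9% to 34.9% for 5/5 steps. The miss rate runs from 100 − 34.9 = 65.1% to 100 − 11.5 = 88.5%.

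**Step 3: the gap that gives 80% power.** This was solved at Arm A rates of 30, 40, 50, 60 and 70%, with Arm B placed at points from A to C. The largest gap needed is 14.2 to 19.6 points at 125 per arm and 15.7 to 21.9 at 100 per arm. At Arm A 50% and 125 per arm it is 16.7 if one arm differs and 19.2 for equal steps; at 70% it is 14.2 and 16.1.

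**Step 4: the attrition sentence, 100 per arm.** Seven of the nine printed rows exceed 80%; 68.7% and 78.7% do not. Steps of 10/10 give 73.7% at Arm A 30% and 50%, and 91.0% at 70%. One arm alone different gives 28.2% to 37.4% for 10 points and 57.9% to 75.7% for 15 points.

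**Step 5: the label.** For 50/65/72.5 the second step is 72.5 − 65 = 7.5, but 10% is printed in both halves. A true 10-point step (50/65/75) would give 96.9% and 92.3%. The printed 91.7% and 84.8% fit the printed rates (92.7% and 85.7%), so the label is the error.

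**The case against.** Four points can be made for the plan.

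- **The table is there to be read.** All arm rates and powers are printed beneath the sentence, and the A-to-C gap is one subtraction away. The awkward wording might only mean that the listed steps start at about 5%. This softens the error without curing it, because the sentence still names 5% as the lower limit and the 79.2% row still falls short with two 9.5-point steps.
- **The ranges depend on the baseline.** Section 3 cites adherence from 16.7% to 92.3%. This is correct, and the figures should carry their condition. At Arm A 85% and 125 per arm, power rises to 20% to 21% for one arm different and 66.5% for 5/5 steps, both still below 80%. A third arm at or next to 100% can push 5/5 steps past 80%, but Table 3 has no such scenario. One arm alone 5 points different stays near 30% even at Arm A 90%.
- **The attrition sentence fits part of the table.** At 100 per arm, the four rows whose printed steps are both at least 10 have 98.8, 84.8, 98.5 and 97.7%, although the 84.8% row owes its place to the wrong label. The two rows below 80% have a step under 10. So the sentence is too general rather than false; 73.7% for 10/10 steps is what limits it.
- **Little changes in practice.** Enrolment and the test stay as they are, and the planned 95% confidence intervals would show how imprecise a null result is. That helps after the event, but the stated sensitivity of the design remains wrong.

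**Conclusion.** The concern holds and needs correcting. The statement of more than 80% power for differences of about 5% is contradicted by the table it cites. Under the plan's own test, with 125 per arm and Arm A between 30% and 70%, power is about 11% to 13% if one arm alone differs by 5 points and 27% to 35% for successive 5-point steps. For 80% power the largest gap must be roughly 14 to 20 points, or 16 to 22 with 100 per arm.

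The result assumes that Table 3 is the three-arm Fisher test, which the reproduction of all 18 entries supports. The attrition sentence is too general. The label on the row 50/65/72.5 is a certain but harmless slip.

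**What to change.** 1. Delete the claim about differences of about 5% and higher.
2. State that Table 3 is the power of the three-arm Fisher test and that its difference column lists adjacent steps, not the largest gap.
3. State that, with Arm A at 30% to 70%, 80% power needs a largest between-arm gap of roughly 14 to 20 points at 125 per arm and 16 to 22 at 100 per arm, depending on baseline and pattern.
4. Qualify the attrition sentence by pattern and baseline: the rows at 100 per arm run from 68.7% to 98.8%, and two of nine are below 80%.
5. Correct the label of 50/65/72.5 to 15%, 7.5% in both halves of Table 3.

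Optionally, add pairwise power beside each row, labelled as such, because the endpoint is used to choose an arm. Unadjusted, over the nine rows at 125 per arm, it is 9.9% to 64.7% for A-B, 20.9% to 72.1% for B-C and 84.1% to 99.9% for A-C. The plan names no pairwise test, so this is a preference and not part of the correction.

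The cost is a few reworded sentences and one label. The stated detectable difference becomes less favourable; enrolment, the primary test and the printed powers do not change.

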Although it is not the primary outcome of this study, the PROs are important secondary outcomes in survivorship care planning. Therefore, we have also calculated the power our sample size has to detect meaningful differences in the PROs across the study arms. PROs will be compared among study arms using linear regression and ANOVA. PRO values at follow-up visits will be modeled as a function of study arm while adjusting for the baseline value and other patient characteristics. Because patients are randomized, there should be no difference in PRO scores or other characteristics between patients at baseline. Given that we will be using a range of different PRO questionnaires and the evidence that differences of one-half a standard deviation are meaningful (Norman et al, Medical Care 2003), these power calculations were conducted to estimate the power to detect differences in standard deviations. For each power calculation, outcomes were simulated from a random normal distribution using the mean (SD) specified in the table for each study arm. Values were compared between arms using ANOVA, and power was calculated as the proportion of simulations that yielded a $p < 0.05$. For each scenario, 1000 simulations were run. As shown in Table 4, we have >80% power to detect meaningful differences in PROs given the sample size planned for the primary analysis of health service outcomes.

Table 4: Power Calculations for Patient-Reported Outcomes

Total Sample Size (A / B / C)				Difference between arms, in standard deviations	Estimated Power
	Arm A	Arm B	Arm C		
125 / 125 / 125	0	0.10	0.45	0.10, 0.45	85.7%
		0.15	0.45	0.15, 0.45	81.6%
		0.4	0.4	0.4, 0.4	82.8%
		0.25	0.45	0.25, 0.45	82.9%

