Receipt of primary/preventive care, avoidance of non-recommended care, and PROs are secondary endpoints, and the analyses are descriptive. The analysis for receipt of primary/preventive care is similar to that for cancer-related follow-up. The endpoint for the avoidance of non-recommended care will be the proportion of patients who do not receive tests that are not recommended in the year following completion of acute treatment. This will be evaluated as a dichotomous variable (did not receive inappropriate care: yes vs. no). For the patient-reported outcomes, we will report the PRO scores by intervention arm at baseline, 6-month, 12-months, and 18-months. The main PRO analysis will be a comparison of the follow-up scores at 12-months by intervention arm adjusting for baseline. We will also compare the PROs at 6 months for Arms B&C vs. Arm A to evaluate the effective of the in-person transition visit vs. just sending the SCP. For the PLANS, we will report mean (SD) scores at the individual item level. For the ASC, we will primarily report the mean (SD) on the two subscale scores, but will also report the individual items and total score. For the FOCUS Information Needs, we will primarily report total number of health information needs (i.e., number of items endorsed “yes”), but will also report individual needs endorsed (dichotomous). For all of the PROs, we will also explore changes longitudinally using appropriate methods (GEE, random effects) and examine any differences in the trends over time between patient subgroups using interaction tests as needed.

d. Early stopping rules.

Early stopping rules are not applicable to this study.

8. Risks

a. Medical risks, listing all procedures, their major and minor risks and expected frequency.

There is a risk of participants feeling tired, bored, or uncomfortable when answering questions about health and health care.

b. Steps taken to minimize the risks.

Participants do not have to answer any question they do not want to answer.

c. Plan for reporting unanticipated problems or study deviations.

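### Table 4's four PRO power figures (81.6 to 85.7%) do not follow from the stated ANOVA method at 125 per arm, which gives 89.9 to 92.5%

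*Combined protocol and SAP*

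**What the plan says.** The PRO power paragraph in section 7.c (Sample size) specifies the calculation in full apart from the SD:

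- Data: "outcomes were simulated from a random normal distribution using the mean (SD) specified in the table for each study arm".
- Test and criterion: "Values were compared between arms using ANOVA, and power was calculated as the proportion of simulations that yielded a" p-value below 0.05.
- Replication: "For each scenario, 1000 simulations were run".
- Scale: Table 4's effect column is headed "Difference between arms, in standard deviations".
- Sample size: 125/125/125 is the only size in Table 4. The text ties it to full enrolment: "we have >80% power to detect meaningful differences in PROs given the sample size planned for the primary analysis of health service outcomes".

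The printed powers for arm means (A, B, C) are 85.7% for (0, 0.10, 0.45), 81.6% for (0, 0.15, 0.45), 82.8% for (0, 0.4, 0.4) and 82.9% for (0, 0.25, 0.45).

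An allowance for dropout is stated only for the primary outcome: "Table 3 also shows the power assuming 20% attrition", which there means 100/100/100. No attrition, adjusted alpha or other SD is stated for Table 4.

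**The concern.** The method, threshold, arm means and sample size are all printed, and the effects are in SD units. The four powers should therefore be reproducible to within the noise of 1,000 simulations, roughly one percentage point. They are not: all four are too low by a similar amount. That points to an input that differs from the text, not to a slip in a single cell.

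At stake is whether Table 4 can be relied on as a record. A reader cannot tell whether it describes power at full enrolment or after dropout, a distinction the plan does draw in Table 3, or whether a different SD or significance level was used.

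**Working it through.** **Inputs.** From the PRO power paragraph and Table 4: three arms, one-way ANOVA, alpha 0.05, n = 125 per arm, and the arm means above. Assumed: SD = 1, because the differences are in standard deviations.

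**Control check on Table 3.** The same kind of recomputation was first applied to the primary-outcome table (3×2 Fisher's exact test, 10,000 runs per row). All 18 rows fall within 1.8 points of the printed value at the printed size, the largest deviation being 2.3 Monte Carlo standard errors. Row 1, for example, gives 80.3% against 79.2% printed at 125 per arm, and 68.8% against 68.7% at 100. The discrepancy is therefore confined to Table 4.

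**Formula.** Power = P(F′ > F crit), where F′ is noncentral F with 2 and 3n − 3 degrees of freedom and noncentrality λ = n × Σ(μᵢ − μ̄)² / SD². At n = 125 the degrees of freedom are 2 and 372, and F crit is 3.02.

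Example, row 1: the mean of 0, 0.10 and 0.45 is 0.1833. The sum of squares is 0.0336 + 0.0069 + 0.0711 = 0.1117, so λ = 125 × 0.1117 = 13.96 and power is 92.5%.

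**Results at 125 per arm.** The Monte Carlo standard error is √(p(1 − p)/1000), with p the computed power.

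| Means A, B, C | Σ(μᵢ − μ̄)² | λ | Computed | Printed | Gap (points) | Gap in MC SEs |
|---|---|---|---|---|---|---|
| 0, 0.10, 0.45 | 0.1117 | 13.96 | 92.5% | 85.7% | 6.8 | 8.2 |
| 0, 0.15, 0.45 | 0.1050 | 13.12 | 90.8% | 81.6% | 9.2 | 10.1 |
| 0, 0.4, 0.4 | 0.1067 | 13.33 | 91.3% | 82.8% | 8.5 | 9.5 |
| 0, 0.25, 0.45 | 0.1017 | 12.71 | 89.9% | 82.9% | 7.0 | 7.3 |

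Summing the squared standardised gaps gives a chi-square of 314 on 4 df, against a 5% critical value of 9.49. Direct simulation of the stated procedure (20,000 runs per row) agrees with the formula: 92.7, 90.8, 91.2 and 89.6%.

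**Which inputs would give the printed values?**

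| Inputs | Row 1 | Row 2 | Row 3 | Row 4 | Chi-square (4 df) |
|---|---|---|---|---|---|
| Printed in Table 4 | 85.7 | 81.6 | 82.8 | 82.9 | – |
| n = 100, SD 1, alpha 0.05 | 85.4 | 83.1 | 83.7 | 81.8 | 3.1 |
| n = 125, SD 1.12, alpha 0.05 | 85.4 | 83.0 | 83.7 | 81.7 | 3.0 |
| n = 125, SD 1, alpha 0.02 | 85.9 | 83.3 | 84.0 | 81.9 | 3.9 |

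Solving row by row, the printed powers imply n of 96 to 103 per arm, or at n = 125 an SD of 1.10 to 1.14, or an alpha of 0.017 to 0.022. With SD 1 and alpha 0.05, every whole number from 96 to 103 per arm keeps the joint chi-square below 9.49.

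**Other readings tried at full enrolment.** The Table 2 arm totals (126/124/125) change the results by about 0.1 point. Reading the differences as successive increments gives about 99% or more in every row. A Kruskal-Wallis test gives about 87 to 91%. None of these recovers the printed figures.

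**The case against.** The strongest objection is that the SD is not visible. The text says the table specifies a mean and SD for each arm, and the heading above the arm columns is blank in the extracted table, so an SD may have been lost in reading the PDF. An SD near 1.12 at 125 per arm would reproduce the printed values as well as 100 per arm does, and there would then be no computing error at the labelled size.

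The part of this that stands is that SD 1 is inferred, not printed, and that the cause cannot be settled from the document. It does not remove the inconsistency. ANOVA power depends on the arm means only through their ratio to the SD, and Table 4 states its differences in SD units. If the simulation used an SD of 1.12 with the tabulated means, the true standardised differences would be smaller than the column says (0.45/1.12 = 0.40), and the heading would be the error. The alpha explanation conflicts in the same way with the printed threshold of 0.05.

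A second objection is that the planned PRO analysis adjusts for baseline, so unadjusted ANOVA power is only an approximation to it. That is true, but the stated simulation is the unadjusted one. Adjusting for a prognostic baseline would normally raise power, so it does not explain lower figures.

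A third objection is that little depends on Table 4. That is accepted and is reflected in the severity.

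**Conclusion.** The concern holds, as a minor point. With the printed sample size, threshold and SD-unit effects, none of Table 4's four powers can be reproduced, and the joint discrepancy is far beyond simulation error. At least one input must differ from what the text and table say. Confidence is high for the non-reproduction, given SD 1. No cause is claimed: 100 per arm is a natural candidate because it is Table 3's attrition size, but a different SD or alpha fits comparably.

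The practical effect is small. The error understates power at full enrolment, and power exceeds 80% in every row at both 125 and 100 per arm. The plan also says that "PROs are secondary endpoints, and the analyses are descriptive". The primary-outcome power in Table 3 reproduces and is not affected.

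**What to change.** Check the PRO simulation code for the sample size, SD and alpha it used, then correct the table accordingly:

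- **If it used 100 per arm:** label the existing values 100/100/100 (20% attrition) and add a 125/125/125 block with about 92.5, 90.8, 91.3 and 89.9%, following Table 3's layout.
- **If it used another SD or alpha:** state it in the text and the table. For an SD other than 1, re-express the differences in true SD units or rerun with SD 1.
- **If it was meant to use 125 per arm, SD 1 and alpha 0.05:** replace the printed values with those above.

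In every case, print the SD in Table 4. The cost is a code check and a table correction. Sample size, design and analysis do not change.
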